4.4 Assignment to Treatment Group/Patient Number

4.4.1 Randomization Procedures

Patients will be randomly assigned in a 2:1 ratio to receive either 0.3 mg/kg patisiran or placebo (normal saline 0.9%).

Patients will be randomized via an interactive response system (IRS). Either designated unblinded site personnel or the pharmacist may request randomization for the patient, but only the pharmacist or unblinded personnel will be allowed to receive the treatment code. The treatment code will be delivered to the unblinded personnel and the pharmacist will use the necessary number of vials for that patient based on their weight.

Treatment arms will be balanced at entry for NIS (5-49 vs 50-130), early onset V30M (<50 years of age at onset) vs all other mutations (including late onset V30M), and previous tetramer stabilizer use (tafamidis or diflunisal) vs no previous tetramer stabilizer use.

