4.5 Early Patient Discontinuation or Withdrawal

Patients are free to discontinue treatment or withdraw from the study at any time and for any reason, without penalty to their continuing medical care.

There are 3 ways for a patient to discontinue treatment and/or withdraw from the study:

- 1) The patient or investigator decides to discontinue study treatment, but the patient agrees to remain in the study and undergo follow-up assessments (as described in [Section 6.3](#)).
- 2) The patient experiences protocol-defined rapid disease progression at Month 9 and elects to discontinue study treatment but remain in the study and return for protocol-specified visits, including follow-up assessment at Month 18 (as described in [Section 4.6](#)).
- 3) The patient decides to no longer participate in the study and withdraws consent.

A patient will be considered to have completed the study if the patient does not withdraw consent from the study and completes protocol-specified procedures up through the 18-month efficacy assessment visit.

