8.5 Adverse Event Reporting Period

AEs and SAEs will be reported according to the following timeframes:

- For patients who complete the study, AEs will be assessed through the End of Study visit on Day 567 or the Follow-up visit on Day 602 (depending whether or not the patient plans to roll over to the open-label extension study). All AEs that occur after the start of study drug administration on Day 0 must be reported in detail on the appropriate CRF page and followed to satisfactory resolution, or through the end of study visit on Day 567 or Day 602 (depending whether or not the patient plans to roll over to the open label extension study) after the last dose of study drug administration. SAEs will be followed through the end of study visit on Day 567 or Day 602 (depending whether or not the patient plans to roll over to the open label extension study), or until satisfactory resolution, or until the SAE is considered by the Investigator to be chronic or the patient is stable, whichever occurs first.
- For patients who meet the criteria for Rapid Disease Progression at Month 9 and receive their last dose of study drug on Day 252 but remain on the study, AEs will be followed through Day 294. Following Day 294, only study-procedure-related AEs will be collected (e.g., skin-biopsy-related AE, venipuncture-related AE). SAEs will be followed by the Investigator until satisfactory resolution or the Investigator deems the SAE to be chronic or stable.

- For patients who withdraw from the study early, ongoing AEs will be followed until resolution or 28 days from last dose, whichever occurs first. SAEs will be followed by the Investigator until satisfactory resolution or the Investigator deems the SAE to be chronic or stable.

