9 STATISTICAL METHODS

9.1 Sample Size

Approximately 200 patients will be enrolled in this study. Of those 200 patients, no more than 40 patients will have a NIS range of 101 to 130. An mNIS+7 progression rate (primary endpoint) in the placebo group of 24 ± 16 points in 18 months was estimated using natural history data from FAP patients. A sample of 154 patients provides 90% power for a 2-sided test with an 8.95 point (37.5%) mean difference between treatment groups in the primary endpoint at 2-sided alpha = 0.05. Assuming a 25% random premature discontinuation rate (due to liver transplantation or other factors), the sample size for this study is approximately 200. Additional patients may be enrolled based on a recommendation to increase the sample size in the interim analysis.

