- c. Patisiran patients who have missing data (either Month 9 or 18) after stopping their study treatment: Patients will no longer benefit from treatment in the future and will have trajectory similar to placebo patients. Therefore, missing data after treatment discontinuation (more than 60 days after last dose of study drug) will be imputed using the data from placebo patients.
2. Patients who die before Month 18 and have missing data: Assuming that deaths observed in the study will likely be related to worsening of disease, the missing data at Month 18 will be imputed by taking random samples from the worst 10% mNIS+7 change scores in the entire population. The imputation will be done for patients from both patisiran and placebo arms.

Missing values will be imputed 100 times to generate 100 complete datasets using procedures as described above. An ANCOVA model will be fit to each “complete” dataset for the change from baseline in mNIS+7 at Month 18. The ANCOVA model will include baseline mNIS+7 as a continuous covariate and treatment arm (patisiran vs. placebo), genotype (V30M vs. non-V30M), age at ATTR onset (Before age 50 vs. After age 50), previous tetramer stabilizer use (Yes vs. No), and region (Western Europe, North America, and Rest of World) as factors. The resulting estimates from the 100 analyses will be combined using Rubin’s formulae, and the 95% confidence interval will be constructed, similar to the procedure described in the MI/ANCOVA section.

More details on the implementation of PMM are discussed in Appendix 7.1.

Including Data Post Alternative Treatment for FAP

The primary analysis will not include mNIS+7 assessments performed after the initiation of alternative treatment for FAP (Section 3.7). Sensitivity analysis including data post alternative treatment for FAP will be conducted using the MMRM model. In this sensitivity analysis, all assessments will be used in the analysis regardless of whether an assessment occurs before or after alternative treatment.

Revised mNIS+7 Total Score Using a Different Algorithm to Handle Missing Components

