7. APPENDICES

7.1. Detailed Statistical Methodology for Pattern Mixture Model

In the PMM analysis, similar to the primary analysis, mNIS+7 assessments performed after the initiation of alternative treatment for FAP will be treated as missing. For non-monotone missing data, the 9-month assessment will be imputed as the treatment group mean. The non-monotone missing data is expected to be rare.

As an initial step, an intermediate mNIS+7 dataset for all mITT patients will be prepared which will include the key variables listed in the table below.

Key Variables	Description
Patient number	Unique subject ID for each patient in mITT population
Treatment arm	Placebo or patisiran
Baseline variables	Including gender, genotype, age at ATTR onset, previous tetramer stabilizer use, region, KPS, FAP stage (I vs. II/III), and cardiac subpopulation.
Baseline mNIS+7 score	
mNIS+7 total score change from baseline at Month 9	Set as missing if a patient does not have 9-month data; If a patient has 18-month mNIS+7 but is missing 9-month (non-monotone missingness), the 9-month value will imputed as the treatment group mean.
On-treatment flag for Month 9	If 9-month assessment is non-missing: If assessment date – last dose date \leq 60 days, then flag = “yes” otherwise flag = “no” If 9-month assessment is missing: If Day 254 (scheduled 9-month visit) – last dose date \leq 60, then flag = “yes” otherwise flag = “no”
mNIS+7 total score change from baseline at Month 18	Set as missing if a patient does not have 18-month data
On-treatment flag for Month 18	If 18-month assessment is non-missing: If assessment date – last dose date \leq 60 days, then flag = “yes” otherwise flag = “no” If 18-month assessment is missing: If Day 554 (scheduled 18-month visit) – last dose date \leq 60, then flag = “yes” otherwise flag = “no”
Death flag	Flag = “yes” if a patient has missing 18-month mNIS+7 and death day \leq 561; otherwise flag = “no”

Step 1: For patients who have missing data and are alive before Month 18: imputation of missing data for the placebo arm and for the patisiran arm during the on-treatment period.

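### New deaths after a patient leaves the study are not ascertained to Month 18, so the pattern-mixture analysis can impute a dead patient as alive, and deaths by arm are incomplete

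*Protocol*

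**What the plan says.** **Protocol.** Section 4.5 gives three ways to stop treatment or leave. The third is "The patient decides to no longer participate in the study and withdraws consent". Sections 4.5.2 and 6.3.1 ask a leaver to attend an Early Withdrawal visit, which is timed to the withdrawal and not to Month 18. Section 8.5 states: "For patients who withdraw from the study early, ongoing AEs will be followed until resolution or 28 days from last dose, whichever occurs first". The next sentence there has the investigator follow SAEs until they resolve or are judged chronic or stable, and Section 8.11 says the same of all SAEs. Under Section 4.6, rapid progressors who also leave the study have no visits after Day 273. The health-status phone calls in Section 7.6.3 cover only patients on the modified schedule. The Month 9 and Month 18 return visits in Section 6.3.2 cover only treatment discontinuers who agree to come back.

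**SAP.** Section 4.3.1.3 has a separate rule for "Patients who die before Month 18 and have missing data": their Month 18 change is drawn at random from the worst 10% of change scores across both arms. Section 7.1 turns this into a death flag, set to yes "if a patient has missing 18-month mNIS+7 and death day" is no later than 561, and to no in every other case. Patients flagged no go through the steps for living patients. Placebo patients are imputed under MAR from placebo data, and patisiran patients more than 60 days past their last dose are imputed from placebo data. Otherwise deaths appear as a count in the AE summary and as a listing (Section 4.6.2).

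**The concern.** The SAP needs a fact that the protocol does not collect for everyone. To separate dead from living patients with a missing Month 18 score, someone must know on or about Day 561 whether a patient who left is alive. No section of either document asks for that, and the flag turns unknown status into alive.

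Two things are at stake. First, the pattern-mixture model is the only planned missing-not-at-random analysis of the primary endpoint. Its death rule rests on the SAP's premise that deaths probably reflect worsening disease, yet an unseen death gets the milder imputation. Second, both documents describe a disease with a life expectancy of 5 to 15 years from symptom onset, and no all-cause count of deaths to Month 18 by arm is planned for all dosed patients. If withdrawal differed between arms, recorded deaths would be counted over unequal follow-up.

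**Working it through.** **1. Flag logic.** Missing Month 18 score with death day 400: flag yes. Missing Month 18 score with no death day on file: flag no. The second patient is handled as alive, whatever actually happened.

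**2. The plan's own figures.** Inputs from Protocol 9.1: "A sample of 154 patients provides 90% power for a 2-sided test with an 8.95 point (37.5%) mean difference between treatment groups"; "in the placebo group of 24 ± 16 points in 18 months"; "primary endpoint at 2-sided alpha = 0.05". Allocation from Protocol 4.4.1: "Patients will be randomly assigned in a 2:1 ratio to receive either 0.3 mg/kg patisiran or placebo".

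- Placebo n = (1.96 + 1.2816)² × 16² × (1 + 1/2) / 8.95² = 50.4, so 51. Patisiran 102; total 153 against 154 stated. A noncentral t calculation at 51:103 gives 90.1% power.
- 154 / 0.75 = 205.3, so 206, against approximately 200 stated.

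The design figures reproduce, and a vital-status check leaves the sample size unchanged.

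**3. Gap between the two imputations.** Take change scores as normal with SD 16 in both arms, means 24 (placebo) and 24 − 8.95 = 15.05 (patisiran), mixed 1:2.

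- Solving (1/3)·P(N(24,16) > c) + (2/3)·P(N(15.05,16) > c) = 0.10 gives c = 39.3.
- The mean above c is 47.1.
- A placebo-type imputation averages 24, so the gap is 47.1 − 24 = 23.1 points.

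This gap is marginal. The imputation also uses baseline mNIS+7, Karnofsky status, FAP stage, cardiac subpopulation and the Month 9 change where available, so a patient already worsening would be imputed above 24 and the gap would be smaller.

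**4. Shift in the pattern-mixture difference.** With 200 patients at 2:1 (133.3 and 66.7):

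- one hidden patisiran death: 23.1 / 133.3 = 0.17 points in favour of patisiran;
- one hidden placebo death: 23.1 / 66.7 = 0.35 points against patisiran;
- five hidden patisiran deaths only: 8.95 would become about 8.1 once reclassified;
- five hidden placebo deaths only: about 10.7;
- two patisiran and one placebo: 2 × 0.1736 − 0.3471 = 0.

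**5. How many hidden deaths.** The documents give no 18-month death rate, so this is a range under assumptions: constant hazard, mean survival L of 5 to 15 years, t = 0.75 to 1.5 unobserved years. Expected deaths = leavers × (1 − exp(−t/L)).

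| Leavers | L = 15, t = 0.75 | L = 5, t = 1.5 |
|---|---|---|
| 10 | 0.5 | 2.6 |
| 25 | 1.2 | 6.5 |
| 50 | 2.4 | 13.0 |

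Fifty is 25% of 200 and an upper bound for patients with no vital status.

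**6. What it would take to matter.** With 154 evaluable patients, SE = 16 × √(1/51.3 + 1/102.7) = 2.74, and 1.96 × SE = 5.36. Starting from 8.95, (8.95 − 5.36) / 0.1736 = 20.7, so about 21 hidden deaths, all on patisiran. The model itself dilutes the effect: if 25% of patisiran patients were imputed from placebo data, it would start from 0.75 × 8.95 = 6.71, and (6.71 − 5.36) / 0.1736 = 7.8, so about 8. Both are rough, and both assume no hidden death on placebo.

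**The case against.** The case for leaving the plan alone has several good parts.

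- **Safety follow-up does not stop at 28 days.** A reader of the Section 8.5 sentence alone might infer that it does. The documents do not support that: SAEs already open are followed to resolution or stability, and under Section 4.5.2 a patient withdrawn for a medical reason stays under the investigator's supervision for safety follow-up. SAP 7.1 does not restrict where a death day comes from, so a death learned of after withdrawal sets the flag. What remains is new deaths that arise outside an open SAE and are not otherwise reported.
- **Late leavers often have a Month 18 score.** SAP 3.9 groups a discontinuation visit with Month 18 if it falls within 3 months of the scheduled assessment, and the Early Withdrawal visit includes mNIS+7. For them the death rule does not apply.
- **The 25% is not loss of vital status.** One might infer that a quarter of patients vanish. Protocol 9.1 assumes premature discontinuation, including for liver transplantation, and Section 4.5.1 encourages those who stop treatment to stay on study.
- **The bias has no fixed direction.** One might infer that it flatters patisiran. It does so only if hidden deaths exceed a 2:1 split towards patisiran; otherwise it cancels or works against the drug.
- **Early mortality may be low.** The 5 to 15 years runs from symptom onset, and entry excludes anticipated survival under 2 years, NYHA class above 2 and Karnofsky below 60%.
- **The remedy is weakest after full withdrawal of consent.** True, but investigators may also withdraw patients (Section 4.5.1) who have not refused contact, and permission can be sought from the rest.

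These points limit the size of the problem. None supplies the missing Month 18 status.

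**Conclusion.** The point holds as a gap between the data the protocol collects and the data a planned sensitivity analysis needs. An unrecorded death in a leaver with a missing Month 18 score is imputed as a living patient's score, and deaths by arm to Month 18 are incomplete.

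A reader might go further and infer that the primary result is at risk. The documents do not support that: the primary MMRM (SAP 4.3.1.1) uses no death flag. Losing significance in the pattern-mixture analysis through this route would need a large and wholly one-sided set of hidden deaths.

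The per-death shifts rest on normality, a common SD of 16, the design means and a placebo-average imputation for the patient concerned. Conditioning on baseline and Month 9 should reduce them for patients who were already deteriorating. The number of hidden deaths and their split by arm cannot be derived from the documents. This is a worthwhile and inexpensive improvement, not a flaw that threatens the trial's conclusion. The mortality count gains from it whatever happens to the pattern-mixture result.

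**What to change.** **Protocol 4.5 and 6.3.** For every dosed patient who leaves the study, ask at withdrawal for permission to check vital status later. Ascertain it once, with date of death, at the time of the scheduled Month 18 visit, by phone, treating physician or public record, as consent and local law allow.

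**SAP.** Derive the Section 7.1 death flag from that record. Report known and unknown vital status, and all-cause deaths to Month 18, by arm for all mITT patients. Add one pattern-mixture run that treats unknown status as death.

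**Cost.** At most about 50 contacts or record checks, a sentence in the consent form, and a few lines and one extra run in the SAP. The downside is a little site work, and status may stay unknown for some patients who withdraw consent; the extra run shows how much that matters.

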4.5.1 Reasons for Treatment Discontinuation or Withdrawal

The Investigator may discontinue treatment or withdraw a patient from the study if the patient:

- Is in violation of the protocol;
- Experiences a serious or intolerable AE;
- Becomes pregnant;
- Requires a prohibited medication (see [Section 5.8](#));
- Requests to discontinue treatment or be withdrawn from the study;
- Is found to be considerably noncompliant with the protocol-required patisiran dosing visits.

A patient may discontinue treatment or be withdrawn from the study if, in the Investigator's opinion, they are unable to continue. The Investigator will also withdraw the patient from the study upon the request of Alnylam, including if Alnylam terminates the study. Upon occurrence of a serious or intolerable AE, the Investigator will confer with Alnylam before discontinuing treatment.

In general, patients who discontinue treatment will be encouraged to remain on the study to complete study assessments, particularly the Month 9 and Month 18 assessments, so that their experience is captured in the final analyses. However, a patient may withdraw consent to participate in the study at any time.

Missing an occasional dose of study drug will not necessarily result in the patient being withdrawn from the study. However, if a patient misses 2 consecutive doses of study drug, the Investigator at the site and the Medical Monitor will determine whether treatment should be discontinued.

4.5.2 Handling of Withdrawals or Patients who Discontinue from Treatment

In the event a patient discontinues treatment, withdraws, or is withdrawn from the study, the CRO Medical Monitor must be informed immediately. If there is a medical reason for withdrawal, the patient will remain under the supervision of the Investigator for protocol-specified safety follow-up procedures.

If a patient discontinues treatment, withdraws, or is withdrawn from the study, the primary reason for discontinuation must be recorded in the appropriate section of the CRF and all efforts will be made to complete and report the observations as thoroughly as possible.

If a patient withdraws or is withdrawn from the study, the site staff is to encourage the patient to complete the Early Withdrawal visit. Patients who withdraw or are withdrawn from the study, or patients who remain on the study and permanently discontinue study treatment for reasons other than rapid disease progression at Month 9 (see [Section 4.6](#)),

will not be eligible to participate in the planned extension study in which patients will receive open-label administration of 0.3 mg/kg patisiran once every 21 days.

4.5.3 Replacements

No replacements will be allowed for patients who withdraw early from the study.

4.6 Discontinuation Due to Rapid Disease Progression

At the 9-month time point, if the clinical adjudication committee determines that a patient is exhibiting rapid disease progression (defined as ≥ 24 point increase in mNIS+7 from baseline [based on an average of 2 measurements] and FAP stage progression relative to baseline), the patient's treating physician will provide the patient with the option of discontinuing study drug and receiving local standard of care treatment for FAP.

Patients who discontinue due to rapid disease progression will remain on study through completion of the 18-month efficacy assessments (blinding will be maintained throughout), following a modified visit schedule as shown in [Table 1-3](#). Patients who complete the 18-month efficacy assessments can elect to participate in an extension study in which patients will receive open-label administration of 0.3 mg/kg patisiran once every 21 days. Patients who discontinue study drug due to rapid disease progression and also decide to withdraw from the study will not have any additional visits after the Day 273 assessments are completed and will not be eligible to participate in the planned extension study.

4.7 Pregnancy and Breastfeeding Restrictions / Contraception Requirements

Women of child-bearing potential must have a negative pregnancy test, cannot be breastfeeding, and must be using 2 highly effective methods of contraception prior to screening, throughout study participation, and for 75 days after the last dose of study drug. Highly effective methods of birth control result in a low failure rate (i.e., less than 1% per year)⁴³. Acceptable forms of effective contraception are defined as follows:

- Hormonal: established use of oral, implantable, injectable, or transdermal hormonal methods of conception;
- Placement of an intrauterine device (IUD);
- Placement of an intrauterine system (IUS);
- Mechanical/barrier method of contraception: condom or occlusive cap (diaphragm or cervical/vault cap) in conjunction with spermicide (foam, gel, film, cream or suppository);

Note: Failure rates indicate that, when used alone, the diaphragm and condom are not highly effective forms of contraception. Therefore the use of additional spermicides does confer additional theoretical contraceptive protection. However, spermicides alone are inefficient at preventing pregnancy when the whole ejaculate is spilled. Therefore, spermicides are not a barrier method of contraception and should not be used alone.

- Surgical sterilization of male partner (with the appropriate post-vasectomy documentation of the absence of sperm in the ejaculate; for female patients on the study, the vasectomized male partner should be the sole partner for that patient);

- Sexual true abstinence: when this is in line with the preferred and usual lifestyle of the patient. Periodic abstinence (e.g., calendar, ovulation, symptothermal, post-ovulation methods) and withdrawal are not acceptable methods of contraception.

Patients should be instructed to use two different forms of effective contraception from the list above. Examples of two forms of highly effective contraception are as follows:

- Oral, implantable, injectable, or transdermal contraceptives in conjunction with condom or diaphragm and spermicide;
- IUD in conjunction with condom or diaphragm and spermicide;
- Surgical sterilization of partner in conjunction with condom or diaphragm and spermicide.

Males (including men who have had vasectomies) with partners of child-bearing potential, must agree to use 1 barrier method (e.g., condom) and 1 additional method (e.g., spermicidal foam, gel, film, cream, or suppository) of contraception throughout study participation and for 75 days (i.e., a whole spermatogenic cycle) after the last dose of study drug. Males must also abstain from sperm donation after the first dose of study drug through study participation and for 75 days after last dose of study drug.

Pregnancy reporting guidelines are provided in [Section 8.12](#).

